#### 4.2.1.1 Basiliximab patients: Prednisolone withdrawal

Corticosteroid withdrawal in the basiliximab arm should begin no later than two weeks after transplantation. The dose should be reduced according to local practice. Reduction beyond 5mg daily would require specific approval from the local investigator, but should not occur between 5-7 months after transplantation (ie, around time of second randomisation). Examples of where complete prednisolone withdrawal may be not be appropriate, include a pre-existing condition that is controlled by steroids (e.g. SLE), recent rejection episode, failure to tolerate other immunosuppression at full-intended doses, a non-favourably matched highly sensitised recipient / re-transplant.

#### 4.2.2 Maintenance treatments

	Month 6: Day +0	Day +1	Day +2	Day +3	Day +4
ALLOCATION TO SIROLIMUS MAINTENANCE					
Tacrolimus	Stop after evening dose 				
Sirolimus		3mg od (unless <60 kg when 2 mg od)	3mg od (unless <60 kg when 2 mg od)	3mg od (unless <60 kg when 2 mg od)	3mg od (unless <60 kg when 2 mg od)
					Trough level (target 6-12 ng/mL reducing to 5-10 ng/mL from 12 months post-transplantation)
MPA (for patients in Campath arm)	360mg bd (reduced to 180mg bd from 12 months post-transplantation)				
MPA (for patients in basiliximab arm)	540 - 720mg bd				
ALLOCATION TO TACROLIMUS MAINTENANCE					
Tacrolimus	Target trough level 5-7 ng/mL				
MPA (for patients in Campath arm)	360mg bd (reduced to 180mg bd from 12 months post-transplantation)				
MPA (for patients in basiliximab arm)	540 - 720mg bd				

 If once-daily tacrolimus is used, stop after morning dose

 If mycophenolate sodium cannot be prescribed for local reasons, a dispensation can be made to allow mycophenolate mofetil to be substituted (see Appendix 9: Mycophenolate dosing for equivalent dosing).

#### 4.2.3 Living donor transplant recipients

If it is standard practice at a centre to commence immunosuppression prior to transplantation in recipients of living donor organs then this is acceptable and should be done according to local practice. In this instance it would not be necessary to stop tacrolimus for the first two post-operative days if allocated to receive CAMPATH-based induction therapy.

#### 4.2.4 Concomitant medications

##### 4.2.4.1 Infection prophylaxis

All patients are to receive prophylactic treatment according to current local practice for:

- Pneumocystis carinii pneumoniae
- Oral fungal infection
- CMV

##### 4.2.4.2 Thrombosis prophylaxis

Thrombosis prophylaxis should be commenced in all patients at the time of transplantation according to local practice.

##### 4.2.4.3 Dose modifications for neutropaenia

Absolute neutrophil count (x 10  /mm  )	MPA  dose			
	Year 1 Induction therapy		After year 1 Induction therapy	
	Campath	Basiliximab	Campath	Basiliximab
> 2.0	360mg bd	540-720mg bd	180mg bd	540-720mg bd
1.0 – 2.0	180mg bd	180mg bd	180mg od	180mg bd
< 1.0	stop	stop	stop	stop

This protocol does not specify any contraindicated medications, but local investigators will remain responsible for the management of the participant including all concomitant medications. The treatment schedules above are intended for guidance for the local investigator, and the detailed implementation remains their responsibility and will not be monitored by the coordinating centre.

### 4.3 Appendix 3: Transplant management

#### 4.3.1 Clinical management decisions

As far as possible, general management of the patient (including rejection episodes, medical and surgical complications, side effects of treatments) remains the responsibility of the doctors responsible for patient care, and this study does not impose unnecessary restrictions on such clinical management decisions.

 If mycophenolate sodium cannot be prescribed for local reasons, a dispensation can be made to allow mycophenolate mofetil to be substituted (see Appendix 9: Mycophenolate dosing for equivalent dosing).

In the case of rejection episodes, a biopsy would be strongly encouraged but not required by this protocol.

#### 4.3.1.1 Surgery

Patients who are receiving sirolimus and require a surgical procedure may, if their managing consultant wishes, stop sirolimus up to one week prior to the procedure and use tacrolimus instead until two weeks after the procedure. At this point they should then switch back to sirolimus therapy (according to the procedure outline above in section 4.2.2).

## 4.5 Appendix 5: Organisational structure and responsibilities

### Principal Investigators

The Principal Investigators have responsibility for:

- the design and conduct of the 3C study
- preparation of the protocol and subsequent revisions
- preparation of Standard Operating Procedures
- design, testing and documentation of all computer systems
- managing the coordinating centre
- organising meetings of the 3C Steering Committee
- publication of study reports

The Chief Investigator has overall responsibility for these.

### Steering Committee

The Steering Committee is responsible for:

- agreement of the final protocol
- reviewing progress of the study and, if necessary, agreeing to changes to the study protocol and/or Standard Operating Procedures to facilitate the success of the study
- reviewing new studies that may be of relevance to the 3C study

### Data Monitoring Committee

The independent Data Monitoring Committee is responsible for:

- reviewing interim data from the 3C study according to the schedule set out in the Protocol
- advise the Steering Committee if, in their view, the randomised comparisons in the 3C study have provided **both** (i) “proof beyond reasonable doubt” that for all, or some specific types, of patient, use of CAMPATH and/or sirolimus is clearly indicated or clearly contraindicated; **and** (ii) evidence that might reasonably be expected to influence materially the patient management of many clinicians who are already aware of the main results of any other trials.

### Coordinating Centre

The Coordinating Centre is responsible for the overall coordination of the 3C study. Its functions include:

- study planning, organisation of Steering Committee meetings
- contractual issues with Local Clinical Centres and budget administration
- design and maintenance of 3C study IT system
- provision of study materials
- assistance with local Research Governance applications
- auditing and monitoring progress of the study and Local Clinical Centres
- responding to technical, medical and administrative queries from the Local Clinical Centres
- liaison with the Data Monitoring Committee, regulatory and other outside agencies
- training Local Clinical Centre staff
- organisation of meetings of collaborators

### **Local Clinical Centres**

The responsibilities of the Local Clinical Centre (LCC) lead investigator and LCC research staff will include:

- obtaining local Research Ethics Committee and Research Governance approval (aided by the Coordinating Centre)
- provision of access to appropriate hospital computer systems
- identification and recruitment of suitable patients
- liaising with consultant colleagues in LCC and referring hospitals
- conducting clinic procedures in accordance with the protocol and standard operating procedures
- dealing with routine enquiries from patients and their families
- obtaining appropriate information to confirm potential study endpoints

#### 4.6 Appendix 6: Schedule of study procedures

		Visit						Questionnaire				
		Transplant surgery	Discharge	Month								
				1	3	6	9	12	24	36	48	60
Check eligibility	•											
Medical history	•	•										
Informed consent	•											
First randomisation	•											
Second randomisation					•							
Quality of life assessment		•	•	•	•	•	•	•	•	•	•	•
Laboratory results	Renal function*	•	•	•	•	•	•	•	•	•	•	•
	Lipid profile†	•			•		•					
	FBC‡	•		•	•	•	•					
	Immunosuppressant level	•	•	•	•	•	•	•	•	•	•	•
	Urine protein:creatinine ratio		•	•	•	•	•	•				

\* serum creatinine

† total cholesterol, HDL-cholesterol and triglycerides

‡ including white cell differential

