#### *3.3.5 Laboratory results*

The results of blood and urine tests from the day the form is completed (or the closest available results) will be recorded. This will include serum creatinine and albumin, full blood count, tacrolimus level and urine protein:creatinine ratio.

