### **3.4 FOLLOW-UP VISITS (at months 1, 3, 6, 9 and 12)**

Following randomisation, patients are scheduled to be seen prior to discharge from hospital following the index admission, then at months 1, 3, 6, 9 and 12. These are timed to coincide as far as possible with the standard follow-up of these patients, so extra visits will be kept to a minimum. Telephone follow-up will be used should the patient be unable to attend a clinic follow-up.

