#### 3.4.3 *Blood results*

At each follow-up visit, results for creatinine and therapeutic drug level monitoring will be recorded, as well as a full blood count, lipid profile (total cholesterol, HDL-cholesterol and triglycerides if available) and urinary protein:creatinine ratio at certain visits. These will be copies of results of routine clinical tests requested by the managing team. See Appendix 6: Schedule of study procedures.

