### 3.5 **SECOND RANDOMISATION (at ~6 months)**

The second randomisation (between sirolimus- and tacrolimus-based maintenance therapy) can occur from 5 to 7 months post-transplantation (ideally to coincide with 6 month follow-up visit). The following exclusion criteria will apply:

- proteinuria >800 mg/day (or protein:creatinine ratio >80 mg/mmol);
- biopsy-proven acute rejection (Banff score >1) in previous month.

(See section 3.5.1 for guidance on the management of patients who are not willing and eligible for second randomisation or whose local investigator does not consider it in their best interests.)

In order to minimise the impact of this exclusion criterion, investigators will be encouraged to monitor proteinuria and treat it appropriately (with ACE inhibitors and/or angiotensin receptor blockers) during the first six months post-transplant surgery.

The second randomisation will be stratified by induction therapy allocation and minimized by prognostically-relevant criteria including graft function, proteinuria and blood pressure.

Investigators should only randomise patients for whom they remain uncertain about the benefits of CNI-based or sirolimus-based maintenance treatment. Patients with reduced graft function (e.g. eGFR <40 mL/min/1.73m^2) will not be routinely excluded, but their events in this subgroup will be monitored closely by the independent Data Monitoring Committee.

Patients will be allocated to either remain on tacrolimus (all patients to have target trough level 5-7 ng/mL) or convert to sirolimus. The target trough level for sirolimus is 6-12 ng/mL for the first six months (patients who received basiliximab induction should be maintained at the upper end of this range) and thereafter 5-10 ng/mL.

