Campath, Calcineurin inhibitor reduction and Chronic allograft nephropathy

Data Analysis Plan for assessing clinical efficacy and safety of sirolimus-based maintenance treatment in the 3C Study

1 Background

This Data Analysis Plan describes the strategy, rationale and statistical methods that will guide assessment of the clinical efficacy and safety of sirolimus-based maintenance therapy in the 3C Study. A separate Data Analysis Plan will describe the assessment of Campath-based induction therapy. All analyses and reports will be prepared by the coordinating centre in the Clinical Trial Service Unit, University of Oxford.

The 3C Study is a randomized trial investigating two strategies to improve long-term outcomes in kidney transplantation. Firstly, it is comparing Campath (alemtuzumab) with basiliximab as the basis of induction therapy. Secondly, it is comparing an elective conversion to sirolimus-based maintenance therapy at around 6 months after transplantation compared to remaining on tacrolimus-based maintenance therapy. Follow-up visits are scheduled at 1, 3, 6, 9 and 12 months after transplantation and will then be followed by annual mailed questionnaires. In addition, all participants will be flagged with various NHS registries.

2 Comparisons of sirolimus-based versus tacrolimus-based maintenance therapy

All comparisons will involve comparing outcome during the defined analysis period among all those participants allocated at the maintenance randomization to receive sirolimus-based induction versus all those allocated to receive tacrolimus-based maintenance therapy (i.e. “intention-to-treat” analyses).^{1, 2} All analyses will be stratified by induction therapy arm.

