3.1 Methods of analysis

The fundamental assessments of efficacy and safety will involve comparisons among all randomized patients in their originally allocated treatment group (i.e. “intention to treat” analyses).^{1, 2} Analyses of categorical outcomes will be based on the first relevant unrefuted event of a particular type (i.e. either confirmed or not refuted during the adjudication process). All time-to-event analyses will be based on the first relevant event, and will use log-rank methods to calculate average event rate ratios (95% confidence intervals) and their associated 2-sided P-values.^{2, 4} Comparisons of continuous outcomes will adjust for the baseline value if available, otherwise two-sample t-tests will be used.

The primary comparison between treatment groups of mean follow-up eGFR at 2 years post-transplantation (ie, on average 18 months post maintenance randomisation) will use analysis of covariance (ANCOVA), adjusted for the baseline value.⁵ The baseline creatinine value used will be the latest value available prior to the maintenance randomisation (including a value from a sample

taken on the day of that randomisation). Any value within 6 months of the anniversary of the date of transplantation will be considered as that year's value. If multiple results are available within this window, the one closest to the anniversary date will be used.

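### The primary eGFR analysis adjusts for only the latest value before the maintenance randomisation, and the imputation model uses none: a modest, avoidable loss of efficiency

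*Protocol*

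**What the plan says.** **What is recorded.** Protocol 3.3.5, on the discharge visit, lists the laboratory results: "This will include serum creatinine and albumin, full blood count, tacrolimus level and urine protein:creatinine ratio". Protocol 3.4 schedules visits at discharge, "then at months 1, 3, 6, 9 and 12". Protocol 3.4.3 adds: "At each follow-up visit, results for creatinine and therapeutic drug level monitoring will be recorded". The "Renal function" row of Appendix 6 agrees.

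**When the maintenance randomisation happens.** Protocol 3.5 allows it from 5 to 7 months after transplantation, ideally at the 6-month visit. A month-3 visit held on schedule therefore always comes before it. A month-6 sample may come before or after it.

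**How the primary analysis adjusts.** Under SAP 3.1 the 2-year comparison "will use analysis of covariance (ANCOVA), adjusted for the baseline value". That value is defined as a single one: "The baseline creatinine value used will be the latest value available prior to the maintenance randomisation", with a sample taken on the day of randomisation allowed. SAP section 2 adds: "All analyses will be stratified by induction therapy arm". No earlier eGFR enters the model.

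**How missing 2-year values are imputed.** SAP 3.2 lists age, sex, transplant type, donor age, baseline proteinuria, a participant's other eGFR values and anything found to be associated with missingness. It rules out eGFR values from before the maintenance randomisation. Failed grafts are scored as eGFR 0.

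**The concern.** One routine creatinine measures graft function with short-term noise. If patients also differ in a lasting underlying level, an earlier value tells us something about 2-year eGFR that the latest value does not. The plan collects that value and leaves it out of the primary model.

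The exclusion in SAP 3.2 is the less expected choice. The ANCOVA relies on the relation between baseline and 2-year eGFR, yet the imputation model is not given the baseline. For participants whose 2-year value is imputed, that relation survives only through the other variables in the model. SAP 3.2 places its main emphasis on the imputed result.

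The width of the primary confidence interval is at stake. The direction of the estimate is not. Values taken before the second randomisation cannot have been affected by it, so adding one cannot bias the comparison.

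**Working it through.** **1. The plan's own figure.** Protocol 2.5 claims more than 90% power at α = 0.05 and more than 80% at α = 0.01. It gives no SD, no proportion re-randomised and no baseline–outcome correlation, so the claim cannot be reproduced. One can only find the largest SD that satisfies it. With 75% adherence the difference is 10 × 0.75 = 7.5 mL/min, and the largest SD is 7.5/(z₁₋α/₂ + z₁₋β) × √(n/2), with n per arm. If 70% of the 800 are re-randomised (n = 280):

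- α = 0.05, 90% power: 7.5/3.24 × √140 = 27.4 mL/min
- α = 0.01, 80% power: 7.5/3.42 × √140 = 26.0 mL/min

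The binding limit runs from 21.9 mL/min (50% re-randomised) to 31.0 (100%). The claim is attainable but cannot be verified.

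**2. Model for the gain (all values assumed).** Split eGFR variance into a stable patient share c, a drifting share a with monthly autocorrelation d, and visit noise. The correlation between months s and t is then c + a·d^|s−t|. Write r₆ and r₃ for the correlations of months 6 and 3 with month 24, and r₃₆ for that between months 3 and 6. Month 6 stands in for the latest value.

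- One covariate: R² = r₆²
- Two covariates: R² = (r₆² + r₃² − 2·r₆·r₃·r₃₆)/(1 − r₃₆²)

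**3. Central example, shares 0.60/0.25/0.15, d = 0.95.**

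- r₆ = 0.60 + 0.25 × 0.95¹⁸ = 0.699
- r₃ = 0.60 + 0.25 × 0.95²¹ = 0.685
- r₃₆ = 0.60 + 0.25 × 0.95³ = 0.814
- R² rises from 0.489 to 0.529
- Residual variance falls from 0.511 to 0.471, a cut of 7.8%

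**4. Failed grafts scored 0.** Suppose a fraction f fails, unrelated to baseline, and working grafts have mean 50 and SD 18 (assumed). Each R² is then multiplied by k = (1 − f)/(1 + f × (50/18)²), where (50/18)² = 7.72.

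- f = 3%: k = 0.788. Residual variance falls from 0.615 to 0.583, a cut of 5.1%. The interval is 1 − √0.949 = 2.6% narrower.
- f = 5%: k = 0.686. Residual variance falls from 0.665 to 0.637, a cut of 4.1%. The interval is 1 − √0.959 = 2.1% narrower.

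**5. Range.** Shares were varied over c 30–65%, a 10–60% and noise 5–25%, with d 0.90–0.97 and r₆ about 0.4–0.74.

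| Setting (c/a/noise, d) | R², one → two values | Cut, no failures | Cut with failures | Interval narrower by |
|---|---|---|---|---|
| 0.35/0.60/0.05, 0.95 | 0.346 → 0.354 | 1.3% | 0.7% (f = 5%) | 0.4% |
| 0.60/0.25/0.15, 0.95 | 0.489 → 0.529 | 7.8% | 4.1–5.1% | 2.1–2.6% |
| 0.65/0.10/0.25, 0.97 | 0.501 → 0.571 | 14.1% | 9.2% (f = 3%) | 4.7% |

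**6. Cases outside that range.** Under pure time-decay (no stable share, no noise) the month-3 value adds nothing: at r₆ = 0.7 the residual variance is 0.510 with or without it. At the other extreme, equal correlation ρ at all times gives a residual variance of 1 − 2ρ²/(1 + ρ) with two values. At ρ = 0.7 that takes 0.510 to 0.424, a 17% cut before failures are counted, but it assumes no drift at all between months 3 and 24.

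**7. In mL/min.** With an assumed 300 per arm and residual SD 15–20, the half-width is 1.96 × SD × √(2/300) = 2.40–3.20. Narrowing it by 2.1–2.6% takes off 0.05–0.08 mL/min. In patients, 600 × (1/0.959 − 1) = 26 to 600 × (1/0.949 − 1) = 32.

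**8. Imputation.** The effect of the SAP 3.2 exclusion is not quantified here, because the documents give no figure for how much 2-year eGFR will be missing.

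**The case against.** ANCOVA on one pre-randomisation value is standard, and the SAP cites a methods reference for it. The estimate is unbiased and the interval valid. The second randomisation is minimised on graft function, proteinuria and blood pressure, and analyses are stratified by induction arm. Stated power already exceeds 90%. The gain is a few per cent of interval width at best and could be nil. All of this stands, and it is why the point is optional. Minimisation and stratification do not, however, supply the information that an earlier eGFR carries.

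Three stronger readings are tempting, and the documents do not support them.

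- **A large amount of precision is certainly being lost.** Adding months 1 and 3 under equal correlation of 0.5–0.8 gives an interval 9–15% narrower. That assumes no decay over time and ignores failed grafts scored 0. The documents give no correlations, so even a non-zero loss is an assumption.
- **Values from months 1, 3 and 6 are all discarded.** Where month 6 precedes randomisation it is normally the value already used, and otherwise it may not be a baseline value at all. The unused values are those from discharge and months 1 and 3.
- **The imputed primary result is biased.** Imputation is stratified by both allocations, uses eGFR values from after the maintenance randomisation, and adds characteristics associated with missingness, which could admit baseline eGFR in some circumstances. The exclusion wastes information and fits poorly with the ANCOVA, but bias is not shown.

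**Conclusion.** The point holds as a modest loss of efficiency. SAP 3.1 leaves recorded pre-randomisation eGFR values unused, and SAP 3.2 withholds even the ANCOVA's own baseline from the imputation model. Adding the month-3 value would cut residual variance by about 1–9%, so the interval would be roughly 0.5–4% narrower, or 4.7% in the most favourable setting tried. This rests on assumed correlations and on 3–5% graft failure unrelated to baseline. Failures concentrated among patients with low baseline eGFR would dilute the gain less. Under pure time-decay there is no gain. Neither the validity of the primary comparison nor its stated power is called into question.

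**What to change.** **SAP 3.1.** Pre-specify two eGFR covariates, both from samples taken before the maintenance randomisation (day of randomisation allowed, as now): the latest value, and the month-3 visit value. If the month-3 value is missing, or is itself the latest value, treat the second covariate as missing and fill it with the mean over both maintenance arms combined. Simple mean imputation is acceptable for a covariate measured before randomisation.

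**SAP 3.2.** Replace the sentence that excludes values from before the maintenance randomisation, so that the same two baseline eGFR values enter the imputation model. The remaining variables can stay as listed.

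**Cost.** One degree of freedom and edits to two SAP sections, with no new data. Both edits should be settled before any comparison by maintenance allocation is seen, so that the choice of covariates cannot be questioned.

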#### 4.7 Appendix 7: Specimen label for CAMPATH

For Clinical Trials Use Only	
CAMPATH, Calcineurin inhibitor reduction and Chronic allograft nephropathy (The 3C Study)	
EudraCT number 2008-008553-27 Sponsor: University of Oxford, UK (Freefone [name])	
For use in trial: to be given intravenously as specified in trial protocol	
Chief investigator: [name]	
Patient name and identification number	Date of supply

#### 4.8 Appendix 8: Guidelines for administration of CAMPATH

##### 4.8.1 Intravenous administration

**Available As:** 30mg/1mL vial (alemtuzumab, MabCampath)

**Beware:** No more than ONE vial per dose is required for this indication. If you believe that more than ONE vial is required, please contact the coordinating centre ([name]) to discuss the dose.

